1.10.2 Africana Culture Group. The control group will focus on learning about and experiencing Africana culture through interactive class discussions, lectures, and hand-on demonstrations. This goal for this group is 150 minutes of contact per week so the social component of the Dance intervention is matched. However, crucially, the control group will not participate in any aerobic activities; the majority of their activities will be conducted in a sitting position. Adherence is also tracked in this group, and study participants are encouraged to attend as many classes as possible of the offered sessions (3 classes per week). Each class is expected to last 60 minutes with 5-10 minutes for taking attendance and making administrative announcements at the beginning/end of the class.

Session Compliance. Participants in the study will be completing the African Dance classes or Culture classes under supervised conditions. We will monitor compliance during the classes by having trainers or staff monitor attendance, duration of the dance, ratings of perceived exertion, and heart rate intensity throughout the class period.

Based on the above, we have operationally defined compliance to the intervention as those participants meeting the prescription of either 150 minutes per week of moderate intensity Dance (Group 1), or 150 minutes per week of Africana Culture class (Group 2). Compliance to these prescriptions will be based on the information gathered from the supervised sessions.

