 2. **Line Orientation:** The examinee is presented with the drawing that consists of 13 equal lines radiating out from a single point to form a semicircular fan-shaped pattern. All lines are numbered (1-13). Below this drawing are two lines that match two of the lines from the array above. The examinee is asked to identify which two lines they match. Ten trials are given, with different sets of test lines on each trial.
- *Language:*
 1. **Semantic Fluency test:** This is a semantic fluency test that is part of the RBANS. In this task, the examinee is given one minute to name as many exemplars as possible from a given semantic category (e.g., Fruits and Vegetables).

2. **Picture Naming:** The examinee is presented with a series of pictured objects and is asked to name each one. A semantic cue is provided only if an object is obviously misperceived.

The following questionnaires will also be completed either during the outcome sessions or taken home by participants to complete. They are administered at baseline and after completion of the intervention:

- Demographics, Health History, and Lifestyle:
 1. Health History
 2. Demographic Questionnaire

We also plan to collect a number of other questionnaires at both time points, including, but not necessarily limited to:

3. MacArthur SES
4. Positive and Negative Affect Schedule (PANAS)
5. Satisfaction with Life Scale (SWLS)
6. UCLA Loneliness Scale
7. The Pittsburgh Fatigability Scale
8. Center for Epidemiology Studies Depression Scale (CES-D)
9. Everyday Cognition Questionnaire (ECOG)
10. McGill Pain Questionnaire
11. PROMIS – Physical and Mental, as well as Global Health items

Session 2: The second session will consist of the fitness assessment.

Staff will begin by obtaining a resting blood pressure and heart rate. As long as blood pressure and heart rate are within the permitted safety guidelines (link to Fitness MOP chapter), the participant will begin the Senior Fitness test (link to Senior Fitness test in MOP chapter). Note that the Senior Fitness Test must be completed prior to the submaximal exercise test in order to limit effects of fatigue on these measures. The participant will rest for a brief period and complete some brief questionnaires related to physical activity behaviors and feelings before moving on to the submaximal exercise test.

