After the completion of the measures and sessions described above the participants will be randomly assigned to one of two groups: (a) The Dance condition will consist of approximately 180 minutes per week of moderate intensity African Dance, or (b) an Africana Culture control condition that will consist of 180 minutes per week of mixed-programming related to African Culture, including art projects, cooking, and films. We will use a computer randomization protocol that will incorporate a verification that all session visits have been completed and data entered into the database. We will use a stratified permuted block randomization algorithm with equal allocation to one of the two groups. The use of this strategy will ensure treatment balance on the two factors of age at study entry ($=<70, >70$) and gender. Once randomized, an assigned staff member will contact the subject via phone with the group information. On this contact, the staff

member will give information such as date, day, time, and location of the subject's first intervention session.

1.10 EXERCISE INTERVENTION GROUPS:

1.10.1 African Dance Group. Participants in the Dance condition will begin by dancing at reduced intensity during the first week of the program and will gradually increase their dancing intensity each subsequent week until they reach 40-60% of their heart rate reserve for all of the dance class. All dance sessions start and end with 5-10 minutes of active stretching for the purpose of warming up and cooling down. As the participants will be low active at baseline, the prescribed intensity will be 50–65% of the maximum heart rate reserve for weeks one to four and 65–80% for the remainder of the program. Participants will be fitted with a Polar Bluetooth Smart heart rate sensor around their chest and be encouraged to dance within their target heart rate zone by fitness staff. Continuous heart rate readings of all participants will be displayed in real-time via the Polar Team app on an iPad or other tablet. Certified exercise instructors will closely monitor attendance, intensity, frequency, and safety. Dance sessions will occur three days/week at one of two study sites for the duration of the intervention.

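### Section 1.10.1 sets two intensity targets for the same dance classes which, read literally, share no value from week 5 onward

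*Combined protocol and SAP*

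**What the plan says.** Section 1.10.1 (African Dance Group) describes intensity twice in one paragraph.

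- First statement: participants "will begin by dancing at reduced intensity during the first week of the program" and then "gradually increase their dancing intensity each subsequent week until they reach 40-60% of their heart rate reserve for all of the dance class". It gives no figure for the first week and no week by which the range is to be reached.
- Second statement, two sentences later: "prescribed intensity will be 50–65% of the maximum heart rate reserve for weeks one to four and 65–80% for the remainder" of the program.

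The same paragraph says participants wear a chest sensor with live display and are "encouraged to dance within their target heart rate zone by fitness staff". It speaks of one zone and does not say which of the two ranges it is.

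Elsewhere the dose is described only by a label. Section 1.9 calls it "approximately 180 minutes per week of moderate intensity African Dance". The Session Compliance text under section 1.10.2 has staff monitor, among other things, "ratings of perceived exertion, and heart rate intensity throughout the class period", and counts a Dance participant as compliant at 150 minutes per week of moderate intensity dance. Neither place gives a numeric range for moderate.

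**The concern.** Both statements cover the same participants in the same supervised classes, and both name heart rate reserve as the scale. They lead to different instructions for most of the program. A staff member coaching to the first statement would hold a participant at or below 60% of reserve. One coaching to the second would, from week 5, want that participant at 65% or more. Classes run at two sites, so each site could follow the protocol and still deliver a different dose.

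Three things depend on the choice: the dose that the Dance arm receives, any report of intervention fidelity, and the compliance classification, which requires minutes at moderate intensity without defining it. When the results are read, the trial should be able to say what intensity was prescribed and how often it was met. The current text does not allow a single answer.

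**Working it through.** **Inputs.** First statement: 40–60% of heart rate reserve (HRR). Second statement: 50–65% in weeks 1–4, then 65–80%. All are from section 1.10.1. Three classes per week for 6 months are from sections 1.0 and 1.10.1. Taking 6 months as 26 weeks is an assumption.

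**Step 1. Literal reading, both on the HRR scale.**

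| Weeks | First statement | Second statement | Shared |
|---|---|---|---|
| 1–4 | reduced start, rising to 40–60% | 50–65% | at most 50–60% |
| 5 onward | at most 60% | 65–80% | none |

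The gap from week 5 is 65 − 60 = 5 percentage points. The midpoints are (40 + 60)/2 = 50% and (65 + 80)/2 = 72.5%. The speed of the ramp does not matter: it rises to 40–60%, so on this reading its ceiling stays below the 65% floor.

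**Step 2. Share of the program.** (26 − 4)/26 = 22/26 = 85% of weeks, and 22 × 3 = 66 of 26 × 3 = 78 classes.

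**Step 3. The gap in beats per minute.** The documents give no resting rates. Assume maximum = 220 − age, ages 60, 70 and 80 (within the eligibility range), and resting rates of 60, 70 or 80. The gap is 0.05 × (maximum − resting). The smallest is 0.05 × (140 − 80) = 3 and the largest is 0.05 × (160 − 60) = 5. At age 70 with resting rate 70, the reserve is 150 − 70 = 80:

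- 40–60% of reserve is 70 + 32 to 70 + 48, or 102–118.
- 65–80% of reserve is 70 + 52 to 70 + 64, or 122–134.

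The two ranges are disjoint in all nine combinations.

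**Step 4. Alternative reading: the second statement means percent of maximum heart rate.** Let r = resting rate / maximum. Then 40–60% of HRR equals (40 + 60r) to (60 + 40r) percent of maximum.

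- From week 5, overlap with 65–80% needs 60 + 40r ≥ 65, so r ≥ 0.125, and 40 + 60r ≤ 80, so r ≤ 0.667.
- At r = 0.40 the first range is 64–76% of maximum, and the shared band from week 5 is 65–76%.
- At r = 0.50 it is 70–80%, and the shared band is 70–80%.
- In weeks 1–4 the 50–65% range meets the first range only at 64–65% when r = 0.40, and lies wholly below it when r = 0.50. That would fit a build-up phase.

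The nine combinations in step 3 have r from 60/160 = 0.375 to 80/140 = 0.571, so all of them overlap from week 5 under this reading.

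**Step 5. Search for a reconciling passage.** None was found. The pilot zone in section 1.2.3 (60–75% of age-predicted maximal heart rate) belongs to the earlier study and is not adopted in 1.10.1. The fitness manual chapter linked in section 1.7.3 is cited for the testing visit, and 1.10.1 does not refer to it.

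**The case against.** The strongest reply is that the second statement contains one wrong word. Speaking of a maximum heart rate reserve is odd. If maximum heart rate was meant, step 4 shows a broadly coherent paragraph: a lower start in weeks 1–4, then a range that overlaps 40–60% of reserve. There is textual support. The pilot expressed its zone as percent of age-predicted maximum and described the 68.3% achieved as moderate intensity, and the treadmill test in section 1.7.3 also uses age-predicted maximum. A weaker reply is that the first statement describes only a run-in that a later progression overtakes. It is also fair to say that staff may hold a single zone in a manual that is not part of these documents, and that the per-protocol analysis is defined by completing the intervention and not by heart rate.

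Much of this stands as a limit on size. The figures of 22 weeks and 66 classes hold only if both statements mean heart rate reserve. No stated analysis, intent-to-treat or per-protocol, invokes the compliance rule. The contradiction itself remains. The text says reserve both times, so the slip reading would itself require a correction. The run-in reading sits badly with a second statement that prescribes 50–65% from week one. An unseen manual cannot make the protocol text consistent.

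**Conclusion.** The concern holds. Section 1.10.1 states two targets for the same classes and the documents do not reconcile them. On the literal reading they share at most 50–60% of reserve in weeks 1–4 and are separated by 5 percentage points from week 5, for 22 of 26 weeks (assuming 26 weeks in 6 months). If the second statement means percent of maximum heart rate, the conflict from week 5 disappears for resting rates between 12.5% and 66.7% of maximum, but the text is then wrong about its scale. On either reading the paragraph needs correcting.

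The consequence is confined to the prescribed dose, fidelity monitoring and compliance classification. The primary intent-to-treat analysis and the power calculation do not use these figures. This should be fixed; it does not threaten the primary comparison. Nothing here favours one range over the other.

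**What to change.** The investigators should reconcile the two statements in section 1.10.1 into one target for each program week. The text should name the scale (heart rate reserve or maximum heart rate) and say how the maximum is obtained. The latter is needed because the treadmill test in section 1.7.3 is submaximal, with an endpoint of 85% of age-predicted maximum, and so is not designed to measure a maximum. The same target should then serve for live coaching and for the meaning of moderate intensity in the Session Compliance text.

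The cost is protocol wording; heart rate is already displayed and monitored in class, so no new data are needed. For classes already held, new wording cannot show what was coached. The investigators should therefore also record which target was applied, at each site and over which period, so that dose and fidelity can be reported.

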1.2.3 Results from a pilot African Dance intervention. We have preliminary data from a pilot sample of 33 older African Americans tested across 2 study waves with an average age of 69.21 (standard deviation = 3.60). One-third of the sample reported a family history of cognitive impairment. The data from this study was collected as part of an Alzheimer's Association-funded study on non-pharmaceutical interventions to reduce disparities in cognitive decline (PI: [name]; NPSASA-14-321093).

We randomized participants into one of two groups – an African Dance group or an Africana Education control group. Participants in both groups completed three 1-hour sessions per week for 6 months. Participants (N=19) in the Dance group learned traditional dances from Guinea and South Africa. The dance class started with ~5 minutes of warm-up and dynamic stretching followed by ~50 minutes of instructor-led dance sequences while continuously moving, and finally ~5 minutes of cool down and static stretching. Resting blood pressure and resting heart rate measurements were taken at the beginning and end of class. Heart rate was monitored continuously throughout the class and recorded every 15 minutes. Rating of Perceived Exertion (RPE) from each participant was also recorded at the end of each class. A trained staff member monitored participants' heart rates to ensure participants remained in the target heart rate zone (60-75% of their age-predicted maximal heart rate (APMHR)) for the duration of the class.

Participants in the Education class (N=14) learned about Africana History in 3 sections organized by time period: pre-colonial, colonial, and post-colonial. The topics covered in each section included culture/way of life/customs, spirituality, ethnicity, language, family structures, rites of passage, political structures, and economy. The format of the class was discussion-based and was led by staff originating from Africa. For each topic, instructors typically lecture or show an educational film for part of the hour. The remaining class time is spent in an instructor-led discussion.

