Sixty-six African American older adults (53 female; Mean age = 69.4 ± 4.9 years) were screened and scheduled for baseline testing in Pittsburgh. Of this group, 48 (~90%) successfully completed the baseline measurements and were subsequently randomized and enrolled. First, we successfully maintained heart rate in our prescribed heart rate zone. On average, participants in the Dance group maintained a heart rate (HR) of 68.3% of their APMHR throughout the intervention classes. Thus, our dance intervention was effective at maintaining a HR intensity

in the target range and can be considered a form of moderate-intensity PA. Second, enrollment and adherence continued to improve with each wave of the intervention so that attendance rates in the last wave were >70% for both groups. Attendance rates improved from the first to the second cohort, and enrollment rose from 7 participants in the Dance group and 3 in the Education group in wave 1, to 12 and 11 participants in these two groups, respectively, in wave 2. Importantly, we learned successful advertising methods and tactics to improve attendance. We plan to implement several strategies to further promote attendance in the present study (e.g., transportation support, raffles, performance summaries). We found that participants were overwhelmingly enthusiastic about both interventions. On average, participants rated the enjoyability of the Dance and Education interventions as 5.0 and 4.6, respectively, on a scale of 1-5. In fact, when asked what they would improve about the intervention, many participants suggested that we make the intervention duration longer.

1.3 STATISTICAL ANALYSIS:

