1.7.1 Phone Screening

During the phone screen, numerous medical history questions will be asked to verify that the subject meets inclusion criteria (see Chapter 2): Inclusion and Exclusion and below for more details). Medical record retrieval will not be used,

nor will be PCP approval be required for participation unless the study staff identifies a potential medical issue that warrants such approval (e.g., a previous cardiac event). Information about safety to exercise will be obtained over the phone (e.g., history of falls). Finally, information regarding metal in the body and history of claustrophobia for MRI safety will be obtained including information about any metallic objects in their body and claustrophobia.

1.7.2 Inclusion and Exclusion Criteria.

Inclusion Criteria:

- African American men and women (race self-identified)
- Between 60-80 years of age at enrollment
- Ambulatory without pain or the assistance of walking devices
- No history of falls or balance problems
- Able to speak and read English
- Available during the times that classes are offered, and able to make at least 80% of offered classes (e.g., no long-term travel plans)
- Reliable means of transportation or willingness to let us develop a transportation plan for them
- Willingness to be randomized to *either* group
- Scores on the TICS or MOCA that indicate no more than mild cognitive impairment (scores 26 or above or 21 and above, respectively)
- No diagnosis of a neurological disease that primarily affects central nervous system function (e.g., dementia, multiple sclerosis, Parkinson's disease).
- No current diagnosis of a psychiatric condition (e.g., a current depression or anxiety disorder).
- Eligible to undergo MRI (not claustrophobic and no metal or history of injury involving metal that could be a safety concern for the MRI)
- Able to complete a submaximal fitness test

Exclusion Criteria:

- Not self-identified as African American
- Not between the ages of 60 and 80 at the time of enrollment
- Not fluent in English
- Not available for at least 80% of times classes are offered
- Not willing to be randomized into either group
- Does not have reliable means of transportation and not open to us assisting them with a transportation plan
- Scores below 26 on the TICS, or below 21 on the MOCA (indicating moderate or severe cognitive impairment)
- Metal in body or history of injury involving metal that isn't approved by an MRI safety committee
- Claustrophobia

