Participants will complete a submaximal graded exercise test on a motor-driven treadmill to assess cardiorespiratory fitness (VO_2). The participant will be fitted with a chest-worn Polar Heart Rate monitor and three ECG electrodes. The test will follow a Modified Balke Protocol in which the speed of the test will be mutually agreed upon by the participant and exercise physiologist. Treadmill speed will remain constant while grade will increase every two minutes.

Before beginning the submaximal test, a second resting blood pressure will be obtained. Only participants with safe blood pressure readings will be allowed to continue.

During the fitness test, the participant's expired air will be collected while walking on the treadmill. The participant will wear a fitted facemask which is connected to a metabolic cart in order to analyze all respiratory gases. This VO₂ test usually takes about 15 - 30 minutes to complete depending on the starting fitness level of the participant. These procedures follow guidelines recommended by the American College of Sports Medicine for graded exercise testing. During the test, heart rate is continuously monitored via the Polar Heart Rate monitor chest strap. Blood pressure readings and Rating of Perceived Exertion (RPE) will also be recorded during every two-minute stage. When the subject reaches the endpoint of the exercise test (85% age-predicted maximal heart rate, RPE ≥ 15 for those prescribed beta-blockers, safety concerns, or participant request), the facemask will be removed and they will undergo a four-minute active cool-down in which they will walk at a slower rate with zero incline grade. After these four minutes, the participant will be helped off of the treadmill and undergo a passive cool-down seated in a chair. The participant's heart rate and blood pressure will be recorded every two minutes throughout the cool-down period. The participant will not be allowed to leave until vital signs return to normal patterns (systolic and diastolic blood pressure within 20 mmHg of resting values and heart rate within 20 beats per minute of resting values).

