The safety of study participants will be monitored throughout the study. Study participants will undergo an extensive screening prior to entering the trial to determine that it is safe for them to participate in the intervention. Safety is continuously monitored during the intervention during three supervised sessions per week. We are aware of the potential for serious adverse events (AEs) to occur with any type of exercise training. As such, the trial will take measures to reduce the risk of any adverse events or serious adverse events from occurring. All individuals involved in human subject's research where exercise training is involved, are trained and certified in CPR and First Aid. Included in the exercise stress testing room is an automated external defibrillator (AED), should it be deemed necessary. Lastly, protocols are currently in place to respond to any adverse events that include contacting emergency response personnel and facilitating their arrival to the correct rooms within the buildings at each intervention site.

The REACT II primary investigator has full responsibility for the safety of study participants. The Data Safety Monitoring Board (DSMB), is responsible for objectively monitoring study data for evidence of adverse effects attributed to the intervention. The DSMB also has the authority to recommend changes or pausing the trial until problems are resolved. All AEs experienced by the participant during the study (starting from consent signing until the end of study outcome collection) are to be documented and reported. Serious adverse events will be reported to the DSMB and the IRB. The REACT II trial will track the occurrence of:

- Serious Adverse Events (SAE)
- Unexpected events
- Unfavorable medical events that occur during intervention sessions

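### On one heart-rate scale, the dance zone from week 5 lies wholly above the pilot's zone, and its upper part lies above the heart rate at which the baseline test stops

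*Combined protocol and SAP*

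**What the plan says.** Section 1.10.1 prescribes dance intensity as "50–65% of the maximum heart rate reserve for weeks one to four and 65–80% for the remainder of the program". Earlier in the same paragraph, participants build up week by week "until they reach 40-60% of their heart rate reserve for all of the dance class". In class they will "be encouraged to dance within their target heart rate zone by fitness staff".

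Two other sections describe heart rate on a different scale, as a percentage of age-predicted maximum:

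- The baseline submaximal test (1.7.3, Session 2) ends at "85% age-predicted maximal heart rate, RPE ≥ 15 for those prescribed beta-blockers, safety concerns, or participant request". Eligibility (1.7.2) includes "Able to complete a submaximal fitness test".
- The pilot (1.2.3) used a "target heart rate zone (60-75% of their age-predicted maximal heart rate (APMHR"). Its result: "On average, participants in the Dance group maintained a heart rate (HR) of 68.3% of their APMHR throughout the intervention classes". From this the protocol concludes that the dance stayed in the intended range and counts as moderate-intensity activity.

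Section 1.12 says of entry to the trial: "Study participants will undergo an extensive screening prior to entering the trial to determine that it is safe for them to participate in the intervention". Sections 1.9 and 1.10.2 still describe the intervention as moderate intensity.

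**The concern.** A percentage of heart rate reserve and the same percentage of maximum heart rate are different heart rates. The protocol never converts one to the other, so the class zone, the test endpoint and the pilot zone look closer than they are.

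Two things are at stake. First, the pilot is the protocol's own evidence that this dance can be done at the intended intensity and that the intensity is moderate. If the trial zone lies above everything the pilot aimed for, that evidence concerns a different intensity. Second, the treadmill test is the only monitored exertion to a set heart rate described before randomisation. If it stops below the top of the class zone, it gives no information about the upper part. There is also an analysis consequence: 1.10.2 counts compliance in minutes of moderate-intensity dance, so the heart rates that count as moderate bear on who is compliant.

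**Working it through.** The documents give no converted figure to reproduce, so the check is a conversion.

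**Inputs from the documents:** 65–80% of reserve from week 5, 50–65% in weeks 1–4, and the other target of 40–60% (1.10.1); test stop at 85% of maximum (1.7.3); pilot zone 60–75% and mean 68.3% of maximum, pilot mean age about 69 (1.2.3); ages 60–80 (1.7.2).

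**Assumptions, not in the documents:** resting heart rate 60–80 bpm; maximum = 220 − age (140–160 bpm), used for both zone and test. As a check, maximum = 208 − 0.7 × age (152–166 bpm).

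**Formula:** the heart rate at fraction p of reserve is rest + p × (max − rest) = p × max + (1 − p) × rest.

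**1. Top of the zone against the test stop.** 0.80 × max + 0.20 × rest > 0.85 × max when rest > 0.25 × max. That is a resting rate above 35–40 bpm (38–41.5 bpm with the other formula).

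**2. Example: age 70, resting 70, maximum 150, reserve 80.**

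| Quantity | Calculation | bpm | % of maximum |
|---|---|---|---|
| Zone, weeks 1–4 | 70 + 0.50 × 80 to 70 + 0.65 × 80 | 110–122 | 73–81 |
| Zone from week 5 | 70 + 0.65 × 80 to 70 + 0.80 × 80 | 122–134 | 81–89 |
| Other target, 40–60% | 70 + 0.40 × 80 to 70 + 0.60 × 80 | 102–118 | 68–79 |
| Test stop | 0.85 × 150 | 127.5 | 85 |
| Pilot zone | 0.60 × 150 to 0.75 × 150 | 90–112.5 | 60–75 |
| Pilot mean | 0.683 × 150 | 102.5 | 68.3 |

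The stop is (127.5 − 70) / 80 = 72% of reserve. The top of the zone is 6.5 bpm above it, and 6.5 / 12 = 54% of the band's width lies above the stop.

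**3. Range over ages 60–80 and resting 60–80.** Share of the band's width above the stop = (0.20 × rest − 0.05 × max) / (0.15 × (max − rest)).

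- Age 60, resting 60: (12 − 8) / 15 = 27%.
- Age 80, resting 80: (16 − 7) / 9 = 100%.
- With the other formula, the same two corners give 3.7 / 15.9 = 23% and 8.4 / 10.8 = 78%.

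**4. Zone against the pilot.**

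- Lowest floor: 0.65 + 0.35 × 60/160 = 78% of maximum. Highest top: 0.80 + 0.20 × 80/140 = 91%. The pilot ceiling was 75%, so the two do not overlap. With the other formula the limits are 77.7% and 90.5%.
- Pilot mean as a share of reserve at age 69 (maximum 151): 0.683 × 151 = 103.1 bpm. At resting 60 this is 43.1 / 91 = 47%; at resting 80 it is 23.1 / 71 = 33%. Both are below the 50% floor for weeks 1–4. With the other formula they are 49.2% and 36.5%.

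**5. The other target in 1.10.1.** 0.60 × max + 0.40 × rest exceeds 0.85 × max only when rest > 0.625 × max, or 87.5–100 bpm. It exceeds the pilot's 75% ceiling when rest > 0.375 × max, or 52.5–60 bpm.

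**The case against.** Most of the opposing case stands, and it sets the limits of the point.

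- **No rule is broken.** Nothing says that training must stay below the test endpoint. Section 1.7.3 gives the purpose of the test as measuring change in fitness. Screening also includes telephone questions on safety to exercise, physician approval where an issue is found, and cardiovascular exclusions. A reader might infer that the protocol contradicts its own safety rule, or that screening as a whole fails. The documents support only a gap in what the exercise test covers.
- **Dancers can comply in the lower part of the zone.** A reader might infer that participants are asked to exceed the tested heart rate for most of each session. Share of band width is not share of time. The floor itself passes the stop only when rest > (0.20 / 0.35) × max = 0.571 × max, which is 80 bpm at age 80 and about 91 at age 60.
- **Not everyone is stopped on heart rate.** A reader might extend the gap to practically every participant. Beta-blocker users stop on perceived exertion, so their heart rate at test end cannot be derived, and their share is not given.
- **One formula is assumed.** With 220 − age for the zone and 208 − 0.7 × age for the test, the example gives a top of 134 against a stop of 135.2, and the excess vanishes. The documents name no formula, but give no reason to mix two.
- **The wording may be a slip.** If percentage of maximum was meant, 80% is below the 85% stop. The text literally says reserve, so this too needs settling.
- **The lower target may be the one in force.** Step 5 shows that the test gap then largely disappears; the pilot mismatch partly remains.
- **Classes are monitored.** Live heart-rate display, certified instructors and perceived-exertion records are real safeguards, and the linked manual chapters, which are not available here, may say more. Monitoring in class does not extend what the pilot or the baseline test showed beforehand.

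**Conclusion.** The point holds as a coverage gap and an inconsistency between sections 1.2.3, 1.7.3 and 1.10.1. The pilot mismatch is the firmer half: under either formula, with resting rates of 60–80 bpm, the whole zone from week 5 is above the pilot's ceiling, and the pilot mean is below the floor of even the first four weeks. The pilot's statements about target range and moderate intensity therefore do not support this zone.

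The test gap is narrower. It concerns the upper part of the 65–80% band, for participants stopped on heart rate, with one maximum used for both zone and test. The lower part is covered for most participants. It also depends on which of the two reserve bands in 1.10.1 applies.

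**What to change.** Revise 1.2.3, 1.7.3 and 1.10.1 together:

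1. Express the class zone, the test endpoint and the pilot zone on one heart-rate scale, naming the maximum-heart-rate formula and the resting measurement used.
2. Resolve the two reserve bands in 1.10.1 in the same edit, and confirm whether reserve or maximum is meant.
3. State how the class zone relates to the heart rate reached in the baseline test, including tests that end early or on perceived exertion.
4. Stop citing the pilot as support for a zone it did not test, and say what moderate intensity means on the chosen scale.

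Which intensity or limit applies is for the investigators and the DSMB to decide. The cost is protocol wording and one round of review. No new data are needed, since age, resting heart rate and the test endpoint are already collected.
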